4.3.3. Patient Training Study Design (Phase III)

Immediately after consent, patients will be administered a baseline self-report survey. The table on the following page shows the anticipated schedule of self-report measures to be completed by patients participating in the Patient Training Study (Phase III) as well as the number of items and estimated length of time needed to complete the survey at both time points. Assessments will primarily be conducted using RedCap forms, which are HIPAA compliant and convenient for participants, particularly for baseline (T1) and 2-month follow-up data (T3), whereas post-intervention (T2) data will generally be collected primarily in-person in clinic immediately following the clinic visit which was audio recorded. However, survey data may be administered using paper-based forms in the case that patients are unable or unwilling to complete online surveys and can be collected either through the mail or in person; telephone collection may also be used if needed to facilitate efficient and timely gathering of follow-up data. Medical data will be collected from medical records and include: stage of disease, dates of diagnosis, surgeries, and treatments, and current and past breast cancer treatments.

We will use block randomization to randomize patients 1:1 to either condition with stratification by (a) metastatic disease (Stage IV) vs. non-metastatic disease (anything other than Stage IV) and (b) education (less than or equal to 12 years of education, i.e., a high school diploma) vs. any more than a high school education (equivalent to more than 12 years of education) to assign 64 patients to the Skills-based training plus menopausal and sexual health resources and 64 patients to the Control condition (menopausal and sexual health resources only).

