The patient training intervention will consist of multiple aspects such as PowerPoint slides with voiceover and audio or video clips, along with a workbook. The materials will be sent to participants using a RedCap link, after consent, completion of baseline surveys, and randomization. Patients will be able to complete the intervention either at home using their own computer or other device, or in-person in a private location at Fox Chase, either in advance of their clinic visit or the day of their clinic visit. This flexibility will allow patients without computer access to participate, while still maintaining a consistent time frame in which the assessments and intervention will be delivered.

Patient Training Study (Phase III) Patient Self-Report Measures					
Measure	# Items	Minutes to Complete	Baseline	Post-Training	2-Month Follow-up
Demographics	7	5	X	-	-
Patient-Provider Communication Self-Efficacy (PEPPI-5)	5	3	X	X	X
Beliefs (Self-efficacy/Outcome expectations) ^{67,75}	18	5	X	X	X
Barriers to discussing sexual health	13	4	X	-	X
Self-Report of Communication During Patient Visit	20	10	-	X	-
Hospital Anxiety and Depression Scale (HADS)	27	10	X	-	X
Dyadic Adjustment (DAS-4) ⁷⁶	4	2	X	-	X
Quality of Life (FACT-B Brief) ⁷⁷	23	10	X	-	X
HRQOL Items	10	4	-	X	-
PROMIS SexFS Brief Profile Version 2 (Female) ⁷⁸	14	5	X	-	X
Information/Help-Seeking ⁷⁹	3	2	X	-	X
Therapeutic Aids ⁸⁰	3	3	X	-	X
Satisfaction with Interaction with Provider ⁸¹	4	2	-	X	-
Program Evaluation (Skills-Based Training patients only)	20	10	-	X	-
Resources Evaluation	6	3	-	X	-
Totals					
- Baseline (T1)	117	49			
- Post-Training (T2)	77	37			
- 2-Month Follow-up (T3)	126	44			

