13.3.3. Analyses

Primary Analyses

Prior to conducting primary analyses, we will generate summaries of all variables. Demographic and medical variables will be summarized using descriptive statistics (means, medians, standard deviations, frequencies, proportion missing, etc.). We will assess the distribution of all continuous measures (particularly outcome measures), and if appropriate, normalizing transformations will be applied.

Generalized linear mixed models with appropriate link and variance functions will test for the effects of patient training on beliefs (self-efficacy, outcome expectancies) over time. We will include intervention arm, indicators for timepoint (T2 and T3 vs T2), and an interaction between time and treatment arm. If the interaction between time and treatment arm is significantly different from zero, we will conclude that the intervention influenced beliefs at follow-up (T2/T3). If linear regression models are appropriate, stratification factors (disease stage, education) will be included as covariates to reduce variance. We will use nested random effects (times within patients, patients within providers) to account for multiple sources of correlation.

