Prior to conducting quantitative analyses, the audio recorded clinic visits will be coded, using a similar strategy as described for the Provider Training Study (Phase II), which centers on the newly developed sexuality dialogue codebook, but can also include other communication behaviors or topics that emerge as important through the coding analyses. To test the hypothesis that patient communication behaviors differ for those in the Skills-based vs. Control conditions, we will use Fisher's exact tests. If a patient asks 1 or more questions during the visit, they will be coded as "yes" for outcome 2A and "no" otherwise. If a patient brings up the topic of sexual health they will be coded as "yes" for outcome 2B. If no one brings up the topic of sexual health, they will be coded as "no". If the provider brings up sexual health, these visits will be excluded from analysis of outcome 2B, as it is impossible to know if the patient may have brought up sexual health if the doctor had not done so. In preliminary data from phase II, these communication behaviors were so rare that Fisher's exact tests will be primarily used. If possible, we will also conduct logistic regression analyses accounting for within-provider correlation using random effects (estimated via generalized linear mixed models, similar to the models described above).

In supplementary analyses, we may examine patient factors that may moderate effects on patient outcomes (e.g., age, partnered status, metastatic disease) by including the moderator, study arm, and study arm by moderator interaction terms in generalized linear mixed models. We may also conduct secondary regression analyses to verify the conclusions of primary models, to assess the sensitivity of inferences to the assumptions of the mixed effects models. For example, we may use Generalized Estimating Equations as confirmatory models, or use logistic or ordinal logistic regressions if the semi-continuous outcome measures cannot be transformed so that the assumptions of the linear regression model are met.

Secondary Analyses

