Feasibility and acceptability of the intervention will be analyzed using descriptive analyses. Recruitment rate is operationalized as the proportion of screened and eligible candidates who choose to enroll on the study. Based on our other sexuality trials, a recruitment rate of $\geq 30\%$ will be considered acceptable. Retention is operationalized separately as the proportion of enrolled study subjects who end up completing all study surveys. A retention rate $\geq 70\%$ will be considered adequate. Acceptability is measured through scores on responses to items in the Program Evaluation form. If $\geq 75\%$ of participants indicate "Satisfied" or "Very satisfied" on item 15 of this scale (the overall satisfaction item) at post-treatment, that will indicate adequate overall acceptability of the program. Other items on this scale will also be

analyzed descriptively and the information will supplement about the other data points on the acceptability of the program.

We will also determine whether the skills-based program effected pre-post differences (T3 – T1) for the secondary outcomes of: sexual function, sexual activity (active vs. not active), patients' communication self-efficacy and outcome expectancies, patients' self-reports of barriers to communicating about sexual health, and patient self-reports of psychological health (Hospital Anxiety and Depression scores) and patient self-reports of QOL (FACT-B total score). Similar to the analyses conducted for primary outcome 1, we will use generalized linear mixed models or hierarchical logistic regression models (if outcome is dichotomous), to determine the effect of the intervention arm on these measures. T2-T1 differences will also be analyzed for the beliefs measures.

Exploratory Analyses

If possible, exploratory analyses will be conducted, where we will look at the number of questions patients ask per visit. We will use Poisson or Negative Binomial models for these count outcomes, and will consider zero-inflated models if appropriate. Additional analyses of other exploratory measures will be conducted using generalized linear mixed models, similar to those performed for Primary aim 1. Also, we will explore potential mediation effects, specifically, whether self-efficacy mediates the intervention effect on belief outcomes. We do not anticipate sufficient power for a formal mediation analysis, but we will gather preliminary estimates of effect sizes which may be used to design future studies.

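### For the repeated self-report outcomes, the optional moderator analysis names arm × moderator where the plan's own definition of the training effect calls for moderator × arm × time, which shrinks the estimated moderation

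*Combined protocol and SAP*

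**What the plan says.** All references are to the combined protocol and SAP.

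- **Effect on beliefs (13.3.3, Primary Analyses).** The model is described as "We will include intervention arm, indicators for timepoint (T2 and T3 vs T2), and an interaction between time and treatment arm", with "nested random effects (times within patients, patients within providers" as random effects. The decision rule is "If the interaction between time and treatment arm is significantly different from zero, we will conclude that the intervention influenced beliefs at follow-up (T2/T3". The training effect is therefore carried by arm × time, not by the arm main effect.
- **Effect on secondary outcomes (13.3.3, Secondary Analyses).** "We will also determine whether the skills-based program effected pre-post differences (T3 – T1) for the secondary outcomes". The models are said to be similar to those for primary outcome 1.
- **Moderators (13.3.3, supplementary analyses).** Age, partnered status and metastatic disease are given as examples. The method is "by including the moderator, study arm, and study arm by moderator interaction terms in generalized linear mixed models". The list contains no time term and no interaction with time. The analysis is optional.
- **Assessments (4.3.3).** The time points are defined through "baseline (T1) and 2-month follow-up data (T3), whereas post-intervention (T2) data". In the measures table, the row "Beliefs (Self-efficacy/Outcome expectations" is marked at all three. Barriers, HADS, FACT-B and the PROMIS sexual function profile are marked at baseline and 2 months only.
- **Communication outcomes 2A and 2B (13.3.1).** These are measured once, at the clinic visit after training.

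**The concern.** A moderator question asks whether the training effect differs between subgroups. Where that effect is arm × time, its variation across subgroups is moderator × arm × time. The term named in the plan is a single number for all assessments. At T1 the training has not been given, so randomisation makes the expected arm difference zero in every subgroup. Averaging that zero with the follow-up differences pulls the estimate towards zero.

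What is at stake is the size of any subgroup difference carried forward. Section 13.3.2 says the additional measures are to generate hypotheses for future studies, and the timeline in 4.3 ends Phase III with a further grant application. A moderation estimate that is too small by a fixed fraction is poor material for that purpose.

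**Working it through.** **Plan's own figure.** Section 13.3.4 gives 64 per arm for a 0.5 SD effect with 80% power and 5% two-sided error. A two-sample t-test gives 63.8, so 64 per arm, with power 0.801. It reproduces. The plan gives no figure for the moderator analysis.

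**Inputs.** N = 128 and 0.5 SD come from 13.3.4. Three assessments (beliefs) or two (T1/T3 outcomes) come from 4.3.3. Exchangeable within-patient correlation follows from the patient random effect in 13.3.3. Assumed, because the documents do not give them: the within-patient correlation rho, total SD 1, a 50/50 moderator, complete data, and a moderation d that is equal at T2 and T3.

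**Is baseline an outcome row?** The time indicators are printed with T2 as both a level and its own reference. T1 is the only reference that makes sense, and it agrees with T3 minus T1 for the secondary outcomes. This is an inference.

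**Expected value of arm × moderator.** With exchangeable correlation and complete data, the term is a contrast of patient means over assessments. Carrying time and arm × time over from the primary model does not change this.

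- Beliefs: (0 + d + d)/3 = 2d/3.
- T1/T3 outcomes as repeated measures: (0 + d)/2 = d/2.

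Rho does not enter. In 20,000 simulated trials with d = 0.50, N = 128 and rho = 0.5, the two-way term averaged 0.334 (three assessments) and 0.251 (two). The three-way contrast averaged 0.497 and 0.496.

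**Missing follow-up.** Suppose a fraction r of patients have every follow-up and the rest have T1 only. With n assessments, m of them after training, the share kept is

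[r·m/(1+(n−1)rho)] / [r·n/(1+(n−1)rho) + (1−r)].

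Over rho 0.3 to 0.7:

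| r | Beliefs | T1/T3 outcomes |
|---|---|---|
| 1 | 0.67 | 0.50 |
| 128/144 (recording rate, used as a stand-in) | 0.61–0.63 | 0.45–0.46 |
| 0.70 (retention threshold in 13.3.3) | 0.50–0.54 | 0.37–0.39 |

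**Models without a baseline row.** For follow-up scores only, change scores, or 2A/2B, the share is 1.0.

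**Power for d = 0.5 SD, N = 128.** The interaction contrast has variance (16/128) × v = 0.125v.

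- Beliefs, arm × moderator: v = (1+2rho)/3. At rho 0.5, z = 0.333/√(0.125×0.667) = 1.155, power 21%.
- Beliefs, 1-df three-way contrast, mean(T2,T3) − T1: v = 1.5(1−rho). At rho 0.5, z = 0.5/√(0.125×0.75) = 1.633, power 37%.
- Beliefs, joint 2-df test of the three-way interaction: non-centrality 1.633² = 2.67 at rho 0.5, power 29%.
- T1/T3 outcomes: v = (1+rho)/2 with expectation d/2, against v = 2(1−rho) with expectation d.

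| rho | Beliefs: arm × moderator | Beliefs: three-way, 1 df | Beliefs: three-way, 2 df | T1/T3: arm × moderator | T1/T3: three-way |
|---|---|---|---|---|---|
| 0.3 | 25% | 28% | 22% | 14% | 22% |
| 0.5 | 21% | 37% | 29% | 13% | 29% |
| 0.7 | 18% | 56% | 46% | 12% | 45% |

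For beliefs, the ratio of expected z values (two-way to 1-df three-way) is √[2(1−rho)/(1+2rho)]. It is 1.00 at rho 0.25, 0.94 at 0.3, 0.71 at 0.5 and 0.50 at 0.7.

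**The case against.** The sentence on moderators may be shorthand. It also leaves out time and arm × time, which the belief model must contain, so it can be read as adding a moderator to whatever model each outcome already has. That is a fair reading, but it does not supply the missing term. With time and arm × time carried over, the named interaction is still constant over assessments.

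Three further objections stand and limit the point.

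- **The term is right for part of what the sentence covers.** The text just before it concerns 2A and 2B, which have one assessment each. The secondary outcomes are described as differences between T3 and T1. If they are analysed as change scores, arm × moderator is correct and the factor of 1/2 does not arise. The reference to models similar to primary outcome 1 points towards repeated measures, but the text does not settle it.
- **A reader might infer that real moderation would be missed because of this term.** The figures do not support that in general. At 0.5 SD and 128 patients, power is low under either term at most correlations. For beliefs the loss is negligible near rho 0.3, where the 2-df version of the three-way test does slightly worse than the term as written. Rho is not in the documents.
- **A reader might infer that the trial would then report equal benefit in all subgroups.** Nothing in the documents says that a non-significant moderator would be read that way.

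**Conclusion.** The point holds for the repeated self-report outcomes, as a minor one. If T1 is an outcome row, the named interaction estimates 2/3 of the true moderation for beliefs. It estimates 1/2 for T1/T3 outcomes if these are fitted as repeated measures. These shares assume complete data, exchangeable correlation and equal effects at T2 and T3, and they do not depend on rho. If follow-up is missing as modelled above, the shares are lower.

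The main harm is the shrunken estimate. Loss of power is secondary, and its size rests on an assumed correlation.

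It would be going too far to say that the moderator analysis is wrong for every outcome, or that the trial's findings are at risk. Outcomes 2A and 2B, change-score models and baseline-adjusted follow-up models are unaffected. The analysis is optional and supplementary, and no primary or secondary conclusion depends on it.

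**What to change.** In 13.3.3, replace the moderator sentence with wording to this effect:

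- For repeated self-report outcomes, moderation is tested by moderator × arm × time with all lower-order terms in the model. A single pre-specified 1-df contrast is used, for example the mean of T2 and T3 minus T1 for beliefs, and T3 minus T1 for the other outcomes.
- Alternatively, follow-up scores are modelled with the T1 score as a covariate, and moderation is tested by arm × moderator.
- For 2A and 2B, arm × moderator is kept.

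The 1-df contrast should be named, because a joint test over both follow-up indicators gives up power (29% against 37% at rho 0.5 for beliefs). In the same edit, correct the reference time point in the belief model and state whether the secondary outcomes are fitted as repeated measures or as change scores.

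The cost is a few sentences of SAP text and a few extra model terms. No new data, patients or visits are needed.

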13.3.4. Sample Size Calculations

The sample size calculations are based on the primary belief outcomes. Based on prior literature,⁹⁰ we assume a standard effect size of .60 on the outcome of patient beliefs. We therefore aim to accrue up to 144 patients (72 per arm) in order to collect an estimated 128 audio recordings (64 per arm) to have 80% power to detect a standard effect of 0.5, with 5% two-sided type-I error.

Other primary outcomes include A) the proportion of visits where the patient asks a question, and B) the proportion of visits where the patient brings up sexual health. Based on preliminary data, we expect these proportions to be low in the control arm (15% and 22%, respectively). We also anticipate that 70% of visits will be informative for outcome B (only visits where the physician does NOT bring up sexual health to be included). Therefore, with sample size of 128 audio recordings, we will have 80% power with 5% 2-sided type-I error to detect rates of 38% for outcome A in the intervention arm versus 15% in the control arm (calculations using Fisher's exact test). For outcome B, assuming 45 informative visits per arm, we will have sufficient power to detect rates of 52% in the intervention arm versus 22% in the control arm.

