13.3. Outcomes and Statistical Analyses for Patient Training Study (Phase III)

13.3.1. Primary Outcomes

- (1) Patients' **self-efficacy** and **outcome expectancies** for communicating about sexual health with their provider, and
- (2) (A) **The proportion of visits in which the patient asks at least one question pertaining to sexual health**, and (B) **the proportion of clinic visits in which the patient raises the topic of sexual health**, both at post-training clinic visit

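### Phase III tests four primary outcomes at a nominal 5% each with no rule linking them; the clearest excess error is in the two belief scores (about 8–10%)

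*Combined protocol and SAP*

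**What the plan says.** The combined protocol and SAP, section 13.3.1, lists these as primary for Phase III: "Patients' self-efficacy and outcome expectancies for communicating about sexual health with their provider"; 2A, "The proportion of visits in which the patient asks at least one question pertaining to sexual health"; and 2B, "the proportion of clinic visits in which the patient raises the topic of sexual health". Section 13.3.4 speaks of the belief outcomes in the plural and then continues "Other primary outcomes include A) the proportion of visits where the patient asks a question", with 2B named next, so four is a fair count.

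Section 13.3.3 tests beliefs in generalized linear mixed models with a time-by-arm interaction and gives this decision rule: "If the interaction between time and treatment arm is significantly different from zero, we will conclude that the intervention influenced beliefs at follow-up (T2/T3". It does not say what follows if one belief score is significant and the other is not, or whether the interaction is one joint T2/T3 test or two. Outcomes 2A and 2B are compared by Fisher's exact test, with logistic mixed models added if possible.

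Section 13.3.4 states error and power outcome by outcome:

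- Beliefs, 64 per arm: "to have 80% power to detect a standard effect of 0.5, with 5% two-sided type-I error".
- 2A, 64 per arm, control rate 15%: "we will have 80% power with 5% 2-sided type-I error to detect rates of 38% for outcome A in the intervention arm".
- 2B, 45 informative visits per arm: "we will have sufficient power to detect rates of 52% in the intervention arm versus 22% in the control arm". No alpha is given.

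No section gives a testing order, an alpha split, an adjustment, or a rule that all outcomes must succeed.

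**The concern.** A 5% error rate attached to each of several tests does not carry over to the set. If a conclusion can rest on whichever of two or more primary results is significant, the chance of drawing it falsely exceeds 5%. The problem is most direct for beliefs. There the plan draws one conclusion, that the intervention influenced beliefs, from two scores, and as written a significant interaction on either would support it.

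At stake is how the primary results of the only randomised phase are read. The research timeline in section 4.3 ends the Phase III row with a manuscript and an R01. A reader of that manuscript could not tell from the plan which pattern of results was to count as support for Hypothesis II or Hypothesis III.

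**Working it through.** **Inputs.** Section 13.3.4: 64 per arm for beliefs and 2A, and 45 per arm for 2B; standard effect 0.5 (0.6 assumed from prior literature); 38% vs 15% for 2A; 52% vs 22% for 2B; two-sided 5% for beliefs and 2A. The documents give no correlations between outcomes, so those below are assumptions.

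**1. Reproduce the plan's power at alpha 0.05.**

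- Beliefs: noncentral t, 126 df, noncentrality 0.5 × √(64/2) = 2.83. Power 80.1%.
- 2A: exact enumeration of the two-sided Fisher test. Power 80.1%.
- 2B: the same method with 45 per arm. Power 80.3%.

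The plan's 80% is reproduced for beliefs and 2A with the full 5% spent on each. The 2B figures also give 80% at 5%, which is the basis for inferring that alpha.

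**2. Nominal error over four tests.** If independent, 1 − 0.95⁴ = 18.5%.

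**3. Actual size of Fisher's test.** Exact enumeration with both arms at the control rate gives 2.8% (0.0279) for 2A at 15% and 64 per arm, and 2.6% (0.0263) for 2B at 22% and 45 per arm. If independent:

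- Four tests: 1 − 0.95² × 0.9721 × 0.9737 = 14.6%.
- Two belief scores: 1 − 0.95² = 9.75%.
- 2A and 2B: 1 − 0.9721 × 0.9737 = 5.3%.

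**4. Allow for correlation.** Simulation of four correlated normal test statistics, with critical values set to the nominal 5% or to the actual sizes above:

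| Assumed correlation within / between pairs | Four tests, nominal | Four tests, Fisher's actual size | Belief pair | 2A/2B pair, actual size |
|---|---|---|---|---|
| 0 / 0 | 18.5% | 14.6% | 9.7% | 5.3% |
| 0.3 / 0.1 | 18.1% | 14.2% | 9.5% | 5.2% |
| 0.5 / 0.2 | 17.1% | 13.5% | 9.1% | 5.0% |
| 0.7 / 0.3 | 15.5% | 12.2% | 8.3% | 4.6% |

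Stronger assumed correlation lowers the four-test figure a little further, to about 11% at 0.9 within and 0.5 between pairs at patient level.

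**5. T2 and T3.** If the interaction is read as two tests per belief score, there are six tests: 1 − 0.95⁶ = 26.5% nominally, or 1 − 0.95⁴ × 0.9721 × 0.9737 = 22.9% with Fisher's actual size, if independent.

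**6. Power under control, at the planned numbers.**

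| Alpha | Beliefs, 0.5 | Beliefs, 0.6 | 2A | 2B |
|---|---|---|---|---|
| 0.05 | 80% | 92% | 80% | 80% |
| 0.025 (first Holm step within a pair) | 71% | 87% | 72% | 70% |
| 0.0125 (first Holm step over all four) | 62% | 80% | 61% | 61% |

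Under a fixed sequence with 80% power at each step, the chance of reaching and passing the second, third and fourth outcomes is 0.8² = 64%, 0.8³ = 51% and 0.8⁴ = 41% if independent.

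**The case against.** The best defence is that the plan never claims 5% across the four outcomes. The 5% is attached to each calculation. Beliefs and behaviours sit under separate Hypotheses II and III in section 2.3, with separate conclusions in section 13.3.3, and the section 4.3 timeline calls Phase III a pilot trial. On that view, pooling all four into one family is a choice the plan did not make.

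Much of this stands, and it rules out three stronger readings that a reader might infer.

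- That the plan promises a trial-wide 5% and breaks it. It states no such rate.
- That the true error is 15–19%. That range gives all four tests a full 5% size. Sections 13.3.3 and 13.3.4 specify Fisher's exact test for 2A and 2B, and at the planned control rates its size is little more than half of 5%.
- That any one significant result of the four would be declared as the training having worked. No such overall claim is written; each conclusion is confined to beliefs or to communication behaviours.

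The defence does not reach the belief scores. They share one hypothesis and one conclusion, and Fisher's conservatism does not touch them. For 2A and 2B that conservatism is a by-product of the test, not a multiplicity rule, and the logistic mixed models planned where possible need not share it. The pilot label is a weak answer: section 13.2.4 omits sample size calculations for Phase II because it is a pilot, whereas Phase III is randomised, formally powered and has a stated decision rule. Sizing the trial on beliefs does not set a testing order.

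**Conclusion.** The point holds in this form: four primary outcomes are tested at a nominal two-sided 5% each (inferred for 2B), and nothing in the plan links them. The chance of at least one false primary finding is at most 18.5% nominally under independence, and about 12–15% for the tests as planned under the assumed correlations in the table. The belief pair carries about 8–10% against the 5% in section 13.3.4; the 2A/2B pair is near 5% as it stands.

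These figures assume one interaction test per belief score, control rates of 15% and 22%, and the planned numbers analysed. The absence of a rule is certain from the text. The size is less certain, because the correlations are assumed and the T2/T3 test is undefined. This should be corrected before analysis; it does not put the design in question.

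**What to change.** In section 13.3.3, define one time-by-arm test per belief score, for example a joint test of the T2 and T3 interaction terms. Then add wording such as: Holm's procedure is applied to self-efficacy and outcome expectancies at an overall two-sided 5%, and separately to 2A and 2B at an overall two-sided 5%; error is controlled within the primary outcomes of Hypothesis II and within those of Hypothesis III, not across all four.

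In section 13.3.4, restate first-step power at alpha 0.025: about 71% for beliefs at 0.5 (87% at the assumed 0.6), 72% for 2A and 70% for 2B. State also that error across all four outcomes can still reach about 1 − 0.95² = 9.8% nominally if the two pairs are independent.

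If 5% control across all four is wanted, use a prespecified fixed sequence instead, with beliefs first because the trial is sized on them. Section 13.3.4 does not rank the outcomes within either pair, so that order is the sponsor's choice. The first outcome keeps 80% power; the second to fourth fall to about 64%, 51% and 41% if independent, and outcomes after the first failure become descriptive.

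The cost is a few sentences, plus either lower stated power or fewer claimable outcomes. No extra patients are needed.
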